5. EFFICACY

All efficacy data will be analyzed by intervention arm, analysis phase and over time (when applicable). The primary analysis set will be the mITT analysis set (see definition in Section 2.3). Selected efficacy endpoints will be also analyzed using the ITT and PP analysis sets, respectively (see definition in Section 2.3). Efficacy assessments over time will be performed at the analysis time points defined in Section 2.1.

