1. INTRODUCTION

This statistical analysis plan (SAP) for the 73763989PAHPB2002 phase 2b trial describes the statistical analyses and definitions to assess the efficacy and safety of study interventions including JNJ-73763989 (200 mg), JNJ-56136379 (250 mg), and Nucleos(t)ide analogs (NA) in hepatitis B e antigen (HBeAg) negative virologically suppressed participants with chronic hepatitis B (CHB). In the rest of the document the abbreviations JNJ-3989 and JNJ-6379 are used to refer to the treatments JNJ-73763989 and JNJ-56136379, respectively.

This study is part of the platform trial PLATFORMPAHPB2001 in participants with CHB. The protocol amendment for 73763989PAHPB2002 constitutes the Intervention-specific Appendix (ISA) that describes all the specific and/or additional features of this study complementing the common design elements of the platform trial described in the Master Protocol.

This SAP is to be interpreted in conjunction with the ISA Amendment-2 finalized on 27 January 2020, and with the Master Protocol Amendment-2 for PLATFORMPAHPB2001 finalized on 27 January 2020.

Due to the global impact of the pandemic Coronavirus Disease 2019 (COVID-19), the study team has decided to define the primary analysis set for efficacy as the modified Intention-to-Treat (mITT) analysis set, which excludes from the ITT set all participants impacted by the pandemic defined as those participants who, because of COVID-19 or similar pandemics related reasons, withdrew prematurely from the study prior to Week 72, or had no efficacy assessment for the primary endpoint.

Details of the pharmacokinetic (PK) and pharmacokinetic/pharmacodynamics (PK/PD) analyses will be described in a separate analysis and modeling plan.

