2.3. Analysis Sets

All randomized analysis set: All participants who were randomized in the study. Participants will be analyzed according to the study intervention they were randomly assigned to.

Intent-to-Treat analysis set (ITT): All participants who were randomized in the study and received at least one dose of study treatment within this ISA. Participants will be analyzed according to the study intervention they were randomly assigned to.

Modified Intent-to-Treat analysis set (mITT): All participants who were randomized in the study and received at least one dose of study treatment excluding those participants impacted by the pandemic defined as those participants who, because of COVID-19 or similar pandemics related reasons, withdrew prematurely from the study prior to Week 72, or had no efficacy assessment for

the primary endpoint. COVID-19 or similar pandemics related reasons may include for example missed visits due to travel restriction, shortage of lab kits at the planned visit, missed collection of blood sample at key time points for the primary efficacy endpoint, etc. Participants will be analyzed according to the study intervention they were randomly assigned to.

Safety analysis set: All participants who received at least one dose of study treatment within this ISA. Participants will be analyzed according to the study intervention they actually received.

Per protocol analysis set (PP): All participants in the ITT analysis set who do **not** have any of the selected major protocol deviations that may affect the assessment of efficacy in terms of the primary endpoint at Week 72. The selected major protocol deviations for efficacy analysis purposes that will be used to identify the participants included in the PP set are described in Section 4.5 and [Attachment 1](#). Participants will be analyzed according to the study intervention they were randomly assigned to.

The PK analysis set: All participants who have received at least one dose of study treatment and have at least one valid blood sample drawn for PK analysis.

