5.3.1.1.6. Flares

The criteria based on blood markers/lab tests for each of the flare types are defined as below.

a) Virologic flare is defined as follows:

Derivation 1. This derivation of virologic flare will be assessed only for those participants who are off-treatment and had HBV DNA<LLOQ at the last observed point on all study treatments.

The start date of a virologic flare is defined as the first date of two consecutive visits with HBV DNA > 200 IU/mL. The end date of the same virologic flare is defined as the first date when HBV DNA value returns to ≤ 200 IU/mL or the date of treatment restart, whichever comes first. Each virologic flare will be categorized based on the confirmed (i.e., two consecutive values) peak HBV DNA above any of the four thresholds within the start and end date of that flare as follows: 100,000 IU/mL, 20,000 IU/mL, 2,000 IU/mL and 200 IU/mL.

Derivation 2. This derivation of virologic flare will be assessed only for those participants who are off-treatment and had HBV DNA \geq LLOQ at the last observed point on all study treatments.

The start date of a virologic flare is defined as the first date of two consecutive visits with HBV DNA \log_{10} increase from end of treatment $> 1 \log_{10}$. The end date of the same virologic flare is defined as the first date when HBV DNA \log_{10} increase from end of treatment returns to $\leq 1 \log_{10}$ or the date of treatment restart, whichever comes first. Each virologic flare will be categorized based on the confirmed (i.e., two consecutive values) peak HBV DNA above any of the three thresholds within the start and end date of that flare as follows: 1 \log_{10} , 2 \log_{10} and 3 \log_{10} .

- 1 (Yes) = confirmed** HBV DNA > peak threshold.
- 0 (No) = at least one off-treatment HBV DNA measurement available and not meeting the criteria of confirmed HBV DNA > peak threshold.
- 2 (Not applicable) = no off-treatment HBV DNA quantitative measurements available.

b) Biochemical flare is defined as follows:

- 1 (Yes) = confirmed** ALT and/or AST $\geq 3x$ ULN and $\geq 3x$ nadir (ie, lowest value observed up to the start of the flare)
- 0 (No) = otherwise

The start date of a biochemical flare is defined as the first date of two consecutive visits with ALT and/or AST $\geq 3x$ ULN and $\geq 3x$ nadir. The end date of the same biochemical flare is defined as the first date when there is a 50% reduction from the peak ALT and/or AST level & $< 3x$ ULN.

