c) Clinical flare is defined as follows:

Clinical flare will be assessed with both derivations specified above for virologic flare.

- 1 (Yes)= confirmed^{**} HBV DNA > peak threshold and confirmed^{**} ALT and/or AST ≥ 3 x ULN and ≥ 3 x nadir (ie, lowest value observed up to the start of the flare).
- 0 (No) = otherwise

A clinical flare occurs when a virologic flare and biochemical flare overlap in time. However, if there is no overlap in time, a clinical flare occurs when a virologic flare ends prior to a biochemical flare starting, and the end date of the virologic flare is within 4 weeks of the biochemical flare start date. The start date of a clinical flare is defined as the minimum start date of the virologic flare and the biochemical flare. The end date of a clinical flare is defined as the maximum end date of the virologic flare and biochemical flare, i.e., the later date of HBV DNA ≤ 200 IU/mL (or ≤ 1 log₁₀) and 50% reduction from the peak ALT and/or AST level.

^{**} Confirmed means that the criterion should be fulfilled at 2 or more consecutive time points or at the last observed time point.

The virologic and clinical flares will be assessed only off-treatment, while biochemical flares will be identified on treatment and off treatment, respectively. On-treatment virologic flares are described as virologic breakthrough in Section 5.3.1.1.7. On-treatment will be defined as the time period in which the participant receives any of the study interventions. Off-treatment will be defined as the period after stopping all study interventions (including NA).

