5.3.1.3.2. Time to Flare

Time to biochemical flare (on- and off-treatment), clinical flare off-treatment, and virologic flare off-treatment will be evaluated.

Time to on-treatment flare will be defined as the number of days between the date of first study intervention intake and the date of the first occurrence of on-treatment flare (i.e. the date of the first on-treatment flare [the first of the two confirmation visits] of each type- the date of first study intervention intake+1). The participants who withdrew early from the study before experiencing on-treatment flare or who did not experience on-treatment flare will be censored at the last available blood markers or liver enzymes assessment at or before EOT.

Time to off-treatment flare will be defined as the number of days between the date of last study intervention intake and the date of the first occurrence of off-treatment flare (i.e. the date of experiencing the first off-treatment[the first of the two confirmation visits] flare of each type- the date of last study intervention intake). The participants who withdrew early from the study before experiencing off-treatment flare or who did not experience off-treatment flare will be censored at the last available blood markers or liver enzymes assessment.

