5.3.2.1.3. Flares

The incidence rate will be calculated and summarized for each type of on-treatment or off-treatment flares (virologic, biochemical and clinical) separately, as well as the overall incidence of participants experiencing at least one flare, regardless of type, by study intervention arm. Additionally, for each participant the total number of flares the participant experienced will be counted by type. Such counts will be used to summarize the distribution of the total number of flares by type and by intervention arm.

For on-treatment biochemical flares, the incidence of flares causing treatment discontinuation will be summarized by intervention arm. Further, for off-treatment flares, the count and percentage of participants who experienced a flare followed by NA re-treatment will be summarized by flare type and intervention arm. Similarly, the incidence of flares followed by the achievement of HBsAg seroclearance (at any time) will be summarized by flare type and intervention arm.

For off-treatment virologic, biochemical and clinical flares, the count and percentage of participants who experienced a flare will be summarized by intervention arm and selected subgroups (i.e. by NA type at study entry, by HBsAg levels at EOT, by HBcrAg levels at EOT). Biochemical flares will also be summarized in the follow-up after NA re-treatment. The cut-offs for HBsAg and HBcrAg levels at EOT are provided in Sections 5.3.1.1.5 and 5.4.1.1.2.

Flares that are associated with signs of liver decompensation will be provided in a listing.

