5.3.2.1.4. NA Re-Treatment Criteria During Follow-Up

A cross-tabulation of participants who actually re-started NA treatment (re-started/not restarted) versus participants who met the above criteria (met/not met) will be presented over time.

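### Flare, NA re-treatment and decompensation-flare outputs default to mITT, so a rule written for HBsAg at Week 72 can discard observed flares

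*SAP*

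**What the plan says.** SAP Section 5 sets the default: "The primary analysis set will be the mITT analysis set (see definition in Section 2.3"). It adds that some efficacy endpoints will also be run on ITT and PP, without naming them. Within Section 5, ITT is specified only for the supplementary estimators of the primary endpoint (5.2.2.3).

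SAP 2.3 builds mITT by removing treated participants on these grounds: "because of COVID-19 or similar pandemics related reasons, withdrew prematurely from the study prior to Week 72, or had no efficacy assessment for". Its last limb refers to the primary endpoint, and SAP Section 1 words that limb the same way: "or had no efficacy assessment for the primary endpoint".

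Four outputs in SAP 5.3 name no analysis set:

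- Flare incidence by arm (5.3.2.1.3).
- The decompensation listing (5.3.2.1.3): "Flares that are associated with signs of liver decompensation will be provided in a listing".
- The NA re-treatment table (5.3.2.1.4): "A cross-tabulation of participants who actually re-started NA treatment", set against those who met the criteria.
- Time to flare (5.3.1.3.2, analysed under 5.3.2.3 by Kaplan-Meier and log-rank).

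The SAP already has some rules for incomplete flare data. For time to off-treatment flare, participants "who withdrew early from the study before experiencing off-treatment flare or who did not experience off-treatment flare will be censored" at their last available value (5.3.1.3.2). For virologic flare, a Not applicable code covers "no off-treatment HBV DNA quantitative measurements available" (5.3.1.1.6). Biochemical and clinical flares have no such code, and anyone not meeting the definition is a No.

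Protocol 9.4.1 makes ITT the primary efficacy set.

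**The concern.** The mITT rule asks whether HBsAg at Week 72 could be observed. Flares are observed on treatment and at every follow-up visit to Week 96, so a missing Week 72 sample says nothing about whether a flare was seen. A participant who stays in follow-up but misses the Week 72 assessment for a pandemic reason could flare, restart NA or decompensate, and still drop out of all four outputs.

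What can be lost is the classified flare, its timing, its link to NA restart or later seroclearance, and its line in the decompensation listing. Single cases matter here. Protocol 2.3.2.2 names flare after stopping NA as a risk, and Protocol 2.3.3 reports that re-treatment criteria were updated after a case of reactivation with subacute hepatic failure.

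**Working it through.** **Which set applies.** Elsewhere the SAP names its set: ITT for subject information (Section 4) and patient-reported outcomes (Section 9), safety for exposure (4.6) and Section 6. Section 5.3 names none for these outputs, so the Section 5 default governs.

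**Who is affected.** SAP 5.3.1.1.6 says: "Off-treatment will be defined as the period after stopping all study interventions (including NA"). Under Protocol 4.1, participants who stop study intervention before Week 48 should continue NA, so they generally have no off-treatment period and could lose only on-treatment biochemical flares. Those mainly affected are pandemic withdrawals between Weeks 48 and 72, and participants who remain in the study without the Week 72 assessment.

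**Inputs.** N = 120, 80:40 (Protocol 9.2). The number excluded, m, is not given; I assume 3, 6 or 12. The share s of those with off-treatment data is assumed to be 0.5 to 1. The documents give no flare rate f for this trial. Protocol 2.1 expects HBV DNA rebound in most patients after stopping NA. It cites a 33-patient cohort with ALT flare in 76%, and virologic relapse by Week 12 in 71% on TDF and 4.5% on ETV. I use f from 5% to 76%. The plan's own power figure (>91%) concerns the primary endpoint and is not touched.

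**Expected flare participants removed** = m × s × f.

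| m | low (s = 0.5, f = 0.05) | high (s = 1, f = 0.76) |
|---|---|---|
| 3 | 0.075 | 2.28 |
| 6 | 0.15 | 4.56 |
| 12 | 0.30 | 9.12 |

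**Chance of losing a rare case**, such as a decompensation flare, when exclusion is unrelated to flare. For one case it is m/120: 2.5%, 5% and 10%. For at least one of four cases it is 1 − C(116, m)/C(120, m): 10%, 19% and 35%.

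**Effect on a rate.** If exclusion is unrelated to flare, the expected rate does not change. Otherwise, let e be the excluded fraction of non-flare participants and RR the relative chance of exclusion for flare participants. The observed rate is f(1 − RR·e) / [f(1 − RR·e) + (1 − f)(1 − e)].

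- f = 10%, RR = 2: 9.8%, 9.5% and 9.0% at e = 0.025, 0.05 and 0.10.
- f = 10%, RR = 0.5: 10.1%, 10.2% and 10.5%.
- f = 76%, e = 0.10: 0.608/(0.608 + 0.216) = 73.8% at RR = 2; 0.722/(0.722 + 0.216) = 77.0% at RR = 0.5.

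Cases can be lost, but rates move by about two percentage points at most over these settings.

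**The case against.** The strongest reply is that these participants are not lost to safety reporting, and that is right. Adverse events (including serious, grade 3 or higher, and ALT/AST events of special interest) and laboratory toxicity grades stay on the safety set (SAP Section 6). NA exposure in follow-up is summarised by arm on the safety set (4.6). The ITT listing of premature discontinuations carries NA re-treatment information (4.1), although someone who stays in the study and misses only Week 72 need not appear in it. The IDMC and the flare panel review the data whatever the analysis set (Section 3). A reader might infer that hepatic events of excluded participants vanish; the documents do not support that. None of these outputs, however, gives classified flare incidence, time to flare or the decompensation listing for all treated participants.

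A second reply is that there is little inference to protect. Protocol 9.4.1.2 plans a stratum-adjusted Mantel-Haenszel comparison for flares, but the SAP's list of endpoints so compared (5.3.2.1) contains only seroclearance, and 5.3.2.1.3 summarises flare incidence by arm. A reader might infer that a planned test of flare incidence is compromised; under the SAP, only time to flare is tested (5.3.2.3). This reply stands.

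Third, moving to ITT alone could dilute biochemical and clinical flare rates, because restored participants without off-treatment data would count as No. This also stands, and the fix has to deal with it.

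Finally, flares might be among the unnamed endpoints to be repeated on ITT. That is possible, but the SAP does not commit to it.

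**Conclusion.** The point holds at low severity. As written, the default analysis set can remove observed, classified flares for a reason unrelated to flares, contrary to the protocol's efficacy set. The size depends on an exclusion count the documents do not give and on an assumed flare rate. The upper end of the table needs 12 exclusions, all with off-treatment data, and a flare rate as high as in one small cited cohort.

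Two broader readings fail. mITT does not drop every withdrawal or missed visit, because only pandemic-related ones qualify. Nor do the documents show biased flare rates, because that needs exclusion to be related to flare, and nothing in them indicates that it is.

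**What to change.** State in SAP 5.3.2.1.3, 5.3.2.1.4 and 5.3.2.3:

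- Flare incidence and classification, the NA re-treatment cross-tabulation and time to flare use the ITT set, with the censoring rule of 5.3.1.3.2 for time to flare. Any mITT version is supplementary.
- The denominator for off-treatment biochemical flare is participants with at least one off-treatment ALT or AST value. For clinical flare, an off-treatment HBV DNA value is also required. This matches the Not applicable code for virologic flare and keeps participants without data from being counted as No.
- The listing of flares with liver decompensation covers all treated participants.

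ITT suits the by-arm outputs better than the safety set, which is as-treated and for which SAP Section 6 rules out inferential comparison. If ITT is restored as the general Section 5 default, only the denominator rule is still needed.

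The cost is a population flag and a denominator rule in existing programs, with no new data. Moving from mITT to ITT can only keep or add cases and listing entries. Percentages may move slightly either way.

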5.1. Analysis Specifications

All efficacy endpoints will be summarized descriptively by study intervention arm. In general, continuous variables will be summarized using descriptive statistics (for example, may include the number of participants, mean, standard deviation (SD), two-sided 90% confidence interval (CI), median, and range). Binary or categorical variables will be summarized using the number and percentage of participants in each category. For time-to-event variables, a summary table including number of participants included in the analysis, number of participants censored, 25th and 75th percentiles and median time-to event will be shown. Descriptive summaries will be provided by stratification factors (i.e. screening HBsAg level [$<1,000$ IU/mL or $\geq 1,000$ IU/mL], race [Asian versus non-Asian] and type of NA [TDF/TAF versus ETV]) for secondary efficacy endpoints. Graphic displays will also be used to summarize the data.

5.1.1. Level of Significance

All statistical hypothesis tests will be based on one-sided alpha level of 0.05, and 90% confidence interval (CI) will be presented, unless otherwise specified.

5.1.2. Data Handling Rules

Those measurements collected from screening visit to the end of study will be handled according to the following rules in [Table 3](#).

Table 3: Data Handling Rules for HBV Virology and Serology Assessments

HBV parameter	LLOQ	ULOQ	Imputed Values	
			If value < LLOQ	If value > ULOQ
HBsAg	0.05 IU/mL	124,925.00 IU/mL w/o dilution	0.025 IU/mL ^(a)	137,417.50 IU/mL w/o dilution ^(b)
		249,750.00 IU/mL with dilution		274,725.00 IU/mL ^(b) with dilution
HBeAg	0.11 IU/mL	1,400.00 IU/mL w/o dilution	0.055 IU/mL ^(a)	1,540.00 IU/mL ^(b) w/o dilution
		7,000.00 IU/mL with dilution		7,700.00 IU/mL ^(b) with dilution
HBcrAg*	$3.0 \log_{10}$ U/mL	7.0 \log_{10} U/mL w/o dilution	2.7 \log_{10} U/mL	$7.7 \log_{10}$ U/mL ^{(b)(c)} w/o dilution
		9.0 \log_{10} U/mL with dilution		$9.9 \log_{10}$ U/mL ^(b) with dilution
HBV DNA	20 IU/mL	170,000,000 IU/mL w/o dilution	If target detected: 15 IU/mL If target not detected: 5 IU/mL	187,000,000 ^{(b)(c)} w/o dilution

Table 3: Data Handling Rules for HBV Virology and Serology Assessments

HBV parameter	LLOQ	ULOQ	Imputed Values	
			If value < LLOQ	If value > ULOQ
HBV RNA*	LLOQ = 4.04 \log_{10} cp/mL LOD = 2.49 \log_{10} cp/mL	NAP	If <LOD or target not detected then 2.19 \log_{10} cp/mL	NAP
Anti-HBs	5mIU/mL	10000.0 mIU/mL	2.5 mIU/mL ^(a)	11000.0 mIU/mL ^(b)

* As new assays become available different data handling rules may apply

Key: NAP=Not applicable

(a) LLOQ/2

(b) ULOQ+(ULOQ/10)

(c) If the original result > ULOQ, then take the re-test value (i.e. diluted result). If the diluted result is not available, use the imputed value indicated in this table

All other viral activity data with values <LLOQ which are not included in the data handling rules above will be imputed by the absolute value divided by 2.

5.2. Primary Efficacy Endpoint

5.2.1. Definition

The primary endpoint, also known as “functional cure”, is the proportion of participants who achieved HBsAg seroclearance at Week 72 (24 weeks after completion of 48 weeks of treatment with all study interventions) without restarting NA treatment.

5.2.2. Main Estimand for the Primary Endpoint

Study Objective: To evaluate the efficacy of the study intervention 24 weeks off-treatment.

Scientific Question: in HBeAg negative, virologically suppressed adult population with chronic HBV infection, what is the benefit of JNJ-3989 200 mg+JNJ-6379+NA (Arm 1) for 48 weeks in terms of functional cure 24 weeks after stopping all study interventions compared with NA alone (Arm 2)?

A) Study Intervention:

- Arm 1: JNJ-3989 (200 mg) + JNJ-6379 (250 mg qd) + NA
- Arm 2: Placebo + Placebo + NA

B) Study Population: HBeAg-negative chronic HBV-infected patients who are virologically suppressed by being treated with NA.

C) Variable: Response status defined as participants who meet the criteria defining functional cure at Week 72 (responders) as in Section 5.2.1

D) Intercurrent events:

- Treatment discontinuation prior to Week 48: if the participant discontinued treatment prior to Week 48 then s/he will be considered non-responder (composite strategy).
- Major protocol deviations affecting efficacy: [Attachment 1](#) identifies the deviations considered intercurrent event. Participants with such deviations and who have missing data for the endpoint will be considered as non-responders (composite strategy). For all other deviations not considered intercurrent events, the data are used regardless of the occurrence of major protocol deviations (treatment policy strategy).
- Deaths prior to Week 72 are handled in a composite strategy as participants who die prior to Week 72 will be considered as non-responders.
- NA re-treatment between Week 48 and 72: the participant will be counted as non-responder (composite strategy).

E) Population-level summary: Difference in proportion of participants with functional cure status at Week 72 between study intervention arms.**5.2.2.1. Main Estimator****5.2.2.1.1. Analysis Methods**

The main estimator is constructed using a Mantel-Haenszel ([Mantel N., et al. 1959](#)) test controlling for stratification factors, i.e., screening HBsAg level ($<1,000$ IU/mL or $\geq 1,000$ IU/mL), race (Asian versus non-Asian) and type of NA (TDF/TAF versus ETV) for the difference in proportions between the intervention arms (Arm 1 minus Arm 2). A 2 sided 90% CI of the difference in proportions will be provided.

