5.2.2.1.4. Missing Data Handling Rule

Participants who withdraw from the study prior to Week 72 will be considered as non-responders.

If a participant remains in the study after experiencing a major protocol deviation (defined for the purpose of efficacy analyses and is an intercurrent event) and has missing Week 72 value, then the imputation to non-response will be applied. If the value for the endpoint at Week 72 is available, then such data will be used to determine their response status.

For the participants still in the study at Week 72 or for participants that have neither discontinued treatment early nor experienced any major protocol violations (defined for the purpose of efficacy analyses and is an intercurrent event), and HBsAg values missing at Week 72, then the primary

method to handle missing data will be the Multiple Imputation (MI) approach ([Ratitch B. et al., 2013](#)) under the assumption of MAR will be applied to a model for continuous HBsAg log values over time.

The MI model will use all available data and be applied to the continuous log-transformed HBsAg values (not the binary endpoint). Of note, also the pre-ICE data for those subjects who experienced an ICE will be included in the MI model; but for these subjects the response status will be applied according to the ICE strategies before running the MI model.

The model will include treatment, the 2 randomization factors (race [Asian versus non-Asian] and type of NA [TDF/TAF versus ETV]) and the available non-missing log-transformed HBsAg (values < LLOQ, TND or TD will be first substituted following rules described in [Table 3](#)) for each scheduled time point (Week) and the following demographic and baseline characteristics ([King G. et al., & Honaker J. et al.](#)): age, gender, and baseline log-transformed value for HBsAg level.

A total of 200 datasets will be generated where both intermittent and monotone missing HBsAg values will be imputed for each subject relying on non-missing data from all other subjects within the same treatment group. Once the 200 completed datasets are generated by filling in the missing data with samples from the imputation model, the primary endpoint response status (binary variable) will be derived using both imputed and observed HBsAg values at Week 72.

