12	Subject did not receive dose of study drug JNJ-3989 within window: Within three weeks of the planned administration JNJ-3989 should be administered, If realized later than three weeks the dose should be skipped and administration of the next planned dose as per visit schedule should be awaited. <Specify duration>	Received wrong treatment or incorrect dose	Yes, if classified as MPD (reviewed case by case)	Yes
13	Subject missed more than 5 JNJ-6379/Placebo doses within a four week period.	Received wrong treatment or incorrect dose	Yes, if classified as MPD (reviewed case by case)	Yes
14	Subject missed NA treatment for more than 5 doses within a four week period.	Received wrong treatment or incorrect dose	Yes, if classified as MPD (reviewed case by case)	Yes
15	Subject received expired study medication <JNJ-3989, JNJ-6379, NA or placebo>.	Received wrong treatment or incorrect dose	Yes, if classified as MPD (reviewed case by case)	Yes
16	Subject continue NAs despite no relevant change in participant baseline status with regards to ALT, HBV DNA levels and/or HBeAg status or without any discussion with the sponsor regarding event that could prevent stopping NA	Received wrong treatment	Yes, if classified as MPD (reviewed case by case)	Yes
17	Subject has event of signs of decreasing liver function based on laboratory findings or clinical findings, but did not start NA treatment	Received wrong treatment or incorrect dose	Yes, if classified as MPD (reviewed case by case)	Yes
18	Subject has confirmed HBeAg seroreversion, but did not start NA treatment.	Received wrong treatment or incorrect dose	Yes, if classified as MPD (reviewed case by case)	Yes
19	Subject has a confirmed post-treatment increase in HBV DNA >2,000 IU/mL and ALT >5 x ULN over a period of at least 4 weeks, but did not start NA treatment	Received wrong treatment or incorrect dose	Yes, if classified as MPD (reviewed case by case)	Yes
20	Subject has a confirmed post-treatment increase in HBV DNA >20,000 IU/mL over a period of at least 4 weeks, but did not start NA treatment	Received wrong treatment or incorrect dose	Yes, if classified as MPD (reviewed case by case)	Yes
21	Subject has confirmed signs of hepatic decompensation <specify> but subject continued study treatment	Developed withdrawal criteria but not withdrawn	Yes	Yes
22	The subject has confirmed HBV virological breakthrough but continued study treatment.	Developed withdrawal criteria but not withdrawn	Yes	Yes

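### The primary estimand asks about response 24 weeks off treatment, but no operating rule makes a participant who completes 48 weeks and never stops the nucleos(t)ide analog (NA) a non-responder when Week 72 HBsAg is observed

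*SAP*

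**What the plan says.** SAP 5.2.2 gives the objective as "To evaluate the efficacy of the study intervention 24 weeks off-treatment" and asks about "functional cure 24 weeks after stopping all study interventions compared with NA alone (Arm 2". SAP 5.3.1.1.6 fixes the term for flares: "Off-treatment will be defined as the period after stopping all study interventions (including NA".

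SAP 5.2.1 defines the endpoint as HBsAg seroclearance at Week 72 with no NA restart. It explains Week 72 in parentheses as "24 weeks after completion of 48 weeks of treatment with all study interventions".

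SAP 5.2.2 D lists four intercurrent events: treatment discontinuation before Week 48, selected major protocol deviations, death before Week 72, and NA re-treatment. On the last it says "NA re-treatment between Week 48 and 72: the participant will be counted as non-responder (composite strategy". Protocol 9.4.1.1 and SAP 5.4.1.1.5 likewise name only re-treatment.

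One form of continuing NA is a listed deviation. Attachment 1 No. 16 begins "Subject continue NAs despite no relevant change in participant baseline status", adds continuation not discussed with the sponsor, and is flagged as an intercurrent event. Under SAP 5.2.2 D a flagged deviation leads to non-response only if the endpoint is missing. SAP 5.2.2.1.4 adds: "If the value for the endpoint at Week 72 is available, then such data will be used to determine their response status".

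The plan expects such participants. Protocol 6.6 follows those who cannot stop NA to Week 96, footnote k of the treatment-phase schedule dispenses NA to them at Week 48, and the follow-up schedule gives them their own visits. SAP Amendment 1 changed the phase-end logic because of them.

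**The concern.** HBsAg negativity on NA does not answer a question about response off treatment. A participant who never stopped has had no time off treatment at Week 72, yet follow-up visits are timed from the last dose of the investigational agents or placebo (Protocol 1.3.2, footnote a; SAP Table 1). The participant therefore gets an ordinary Week 72 value.

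If the rules do not say how to score this participant, two analysts can score the same record differently on the primary endpoint. The sponsor's central study team is unblinded at the Week 48 interim analysis, before all Week 72 statuses exist. A rule left unwritten would be settled when that team can know the arm.

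**Working it through.** **Rule check.** Take a participant who completes 48 weeks, stays on NA throughout and has observed HBsAg below the quantification limit at Week 72.

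| Rule | Source | Applies? |
|---|---|---|
| Treatment stopped before Week 48 | SAP 5.2.2 D; Protocol 9.4.1.1 | No, 48 weeks completed |
| Death before Week 72 | SAP 5.2.2 D | No |
| Study withdrawal before Week 72 | SAP 5.2.2.1.4; Protocol 9.4.1.1 | No |
| NA restart or re-treatment, Weeks 48 to 72 | SAP 5.2.1, 5.2.2 D; Protocol 9.4.1.1 | No, NA never stopped |
| Flagged deviation (No. 16) | SAP 5.2.2 D, 5.2.2.1.4 | Only if the value is missing; here it is observed |

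No rule gives non-response, whether continuation was unjustified or agreed.

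Now let the Week 72 value be missing. An unjustified continuer is a non-responder. Continuation for a relevant change and discussed with the sponsor is not a listed deviation. The multiple-imputation clause opens "For the participants still in the study at Week 72 or for participants that have neither discontinued treatment early" and covers missing Week 72 HBsAg, so in the main estimator this participant's status is imputed.

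**Comparison inside the SAP.** Partial cure (5.4.1.1.1) and the marker thresholds (5.3.1.1.3) each state two conditions: interventions stopped, and no NA re-treatment. The primary endpoint carries only the second as an operating condition.

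**Size.** Inputs from SAP 1.4: 80 versus 40, one-sided 0.05, control 5%, difference 20 points (25% versus 5%), power above 91%. With x and y responders and t = x + y, the unstratified Mantel-Haenszel statistic is

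z = (x − 80t/120) / √[80·40·t·(120 − t) / (120²·119)].

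Power is the sum of the binomial probabilities of all (x, y) with z ≥ 1.645. At 25% versus 5% this gives 0.917, which reproduces the plan's figure.

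The number of continuers is not in the documents. Assume that the same share c of would-be responders in each arm is on NA at Week 72. Scoring them as failures gives p₁ = 0.25(1 − c) and p₂ = 0.05(1 − c).

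| c | Difference (points) | Power | On-NA responders, active (80 × 0.25 × c) | Control (40 × 0.05 × c) |
|---|---|---|---|---|
| 0 | 20.0 | 0.917 | 0 | 0 |
| 1% | 19.8 | 0.914 | 0.2 | 0.02 |
| 2.5% | 19.5 | 0.909 | 0.5 | 0.05 |
| 5% | 19.0 | 0.900 | 1.0 | 0.1 |
| 10% | 18.0 | 0.879 | 2.0 | 0.2 |

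**Fixed counts.** At the planned counts, 20/80 versus 2/40, the one-sided p is 0.0004 (Wald, unpooled variance) or 0.0039 (the score statistic above). Reclassifying four active responders gives 16/80, a difference of 20.0% − 5.0% = 15.0 points, with p = 0.0039 (Wald) or 0.015 (score). Against 2/40, one participant decides significance only at the boundary: from 11 to 10 active responders for Wald (0.045 to 0.069), or from 13 to 12 for score (0.040 to 0.055).

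**The case against.** The best counter-argument is that the definition already excludes a continuer. NA is a study intervention, SAP 5.2.1 refers to completing all of them, and someone still taking NA has not done so. On that reading SAP 5.2.2.1.4 only feeds HBsAg into the definition, and no intercurrent-event rule is needed. This is a fair reading and probably the intended one. But the parenthesis can equally be a gloss on what Week 72 means, and no intercurrent-event or data rule puts the requirement into effect. For No. 16 the written strategy is to use the observed value. The ambiguity therefore stands.

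Using observed data after continuation could also be a deliberate treatment-policy choice. That is legitimate, but the objective could not then be described as off-treatment.

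A reader might infer more than the documents support:

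- **That the primary result favors the active arm.** Investigators are blinded to arm, and post-baseline HBsAg is withheld from them until follow-up Week 2 (Protocol 8.1). Nothing suggests unequal continuation. If shares did differ, the net direction is unknown.
- **That planned summaries hide continuers.** SAP 4.1 reports disposition by treatment, 4.5 lists major deviations, 4.6 computes follow-up NA exposure from doses in that phase, and 5.3.1.1.8 identifies restarts from the NA administration CRF page. How a continuer is coded there is not stated. What is missing is a table linking continuation to Week 72 HBsAg status.
- **That SAP 5.4.1.1.4 has the same gap.** It refers to 24 weeks after the end of study intervention, which Protocol 10.1 ties to the last administration. That can be read as requiring NA to be stopped; it needs clarifying.

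The secondary endpoint of seroclearance 24 weeks after stopping all interventions partly answers the question, but it does not decide the primary result. A rule may also exist in the Data Presentation Specification, which is not among the documents.

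**Conclusion.** The point holds as a gap between the estimand's objective and its operating rules. It is not proof that the plan intends to count on-NA responses. For completers who do not stop NA, an HBsAg-negative result at Week 72 can be scored as functional cure under the written rules, and after agreed continuation a missing value is imputed.

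The expected effect is small. Under equal assumed shares of 1% to 10%, the difference falls by 0.2 to 2.0 points and power by 0.003 to 0.038, and the planned result survives a few reclassifications. These shares are assumptions with no source in the documents, and the true number may be zero. The calculation is unstratified. The case for change rests on matching the rule to the question and fixing it in writing. It should be fixed, with medium confidence.

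**What to change.** In SAP 5.2.1, 5.2.2 D and 5.2.3 D, state that a responder must have stopped NA at Week 48. Make NA continued beyond Week 48 an intercurrent event handled as non-response (composite strategy), whether or not Week 72 HBsAg is available. Allow a short tolerance for late stopping, with its length fixed in advance by the sponsor. Say that this overrides the observed-data rule in 5.2.2.1.4 for Attachment 1 No. 16, and derive the event from the NA administration CRF page.

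Align Protocol 9.4.1.1, SAP 5.4.1.1.5 and the Week 96 endpoint, and clarify SAP 5.4.1.1.4. Tabulate continuers by arm with their Week 72 HBsAg status. Because the central team is unblinded at the Week 48 interim analysis, a rule added after that point is open to challenge, so show the primary result under both classifications.

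The cost is a sentence in each place and one small table from data already collected. The drawback is that a participant kept on NA for a clinical reason counts as a failure even if HBsAg-negative, so the response rate may be slightly lower. This is an analysis classification only and changes no clinical rule on stopping NA.
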